Subjects will then be randomized using a computer-generated list and opaque, sealed envelopes to one of two treatment groups: (blocks of 4, stratified for unilateral vs. bilateral surgery): (1) Pecs-2 or (2) paravertebral block. All blocks will be placed by a regional anesthesia fellow or resident under the direct supervision and guidance of a regional anesthesia attending (or by the attending themselves).

For paravertebral blocks, a total of 18 mL of ropivacaine 0.5% with epinephrine will be administered per side (90 mg). An equivalent mass of ropivacaine will be administered for the Pecs-2 blocks (90 mg), but since more volume is required (30 mL per treated side), the concentration will be decreased to 0.3% ropivacaine (with epinephrine). Therefore, for bilateral procedures, 90 mg will be administered bilaterally. The area of needle insertion will be cleaned with chlorhexidine gluconate and isopropyl alcohol. All blocks will be placed using standard UCSD ultrasound-guided techniques as previously described.³

For Pecs-2 blocks and as described by Bashandy and Abbas,³ the needle will be advanced to the tissue plane between the pectoralis major and minor muscles at the vicinity of the pectoral branch of the acromiothoracic artery where 10 mL of local anesthetic will be deposited (Figs. 1-4). In a similar manner, 20 mL will be deposited at the level of the third rib above the serratus anterior muscle with the intent of spreading injectate to the axilla.

For paravertebral blocks, ropivacaine 0.5% 9 mL will be administered at each of two levels per side: the T3 and T5 levels for sides without axillary involvement; and at the T2 and T4 level for sides with axillary involvement.

[figure not shown]

FIGURE 1. Image of the probe position and needle direction from medial to lateral during Pecs I block.³⁰

FIGURE 2. Pecs I block ultrasound view. ax.a indicates axillary artery; p., pectoral branch of thoracoacromial artery.

FIGURE 3. Ultrasound image of needle tip at the plane of Pecs I block between the 2 pectoral muscles (arrows indicate the needle).³⁰

FIGURE 4. Local anesthetic spread between the 2 pectoral muscles. The arrow is pointing to the needle. LA indicates local anesthetic.

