Statistical methods. Descriptive statistics will be provided by arm and in aggregate. Baseline characteristics of arms will be compared using the Wilcoxon-Mann-Whitney and Fisher's Exact tests. Key characteristics that are significantly different ($p < 0.05$) will be included as covariates in the analysis models.

Primary aim. We will test the noninferiority of the serratus nerve block compared to the paravertebral nerve block. The 95% confidence interval (CI) associated with the Wilcoxon-Mann-Whitney test will be derived for the group difference (paravertebral minus serratus) in median pain scores within the recovery room. If the lower limit of the 95% CI is greater than -1.25, we will conclude noninferiority. If there are significant differences between the groups in any key characteristics, these characteristics will be included as covariates in a linear model. The same noninferiority margin (-1.25) will be applied to the 95% CI for the covariate adjusted group difference in mean pain derived from the linear model.

The noninferiority of the serratus nerve block with regard to total opioid consumption within the operating and recovery rooms will be tested in the same manner as pain, i.e. comparing the limits of a 95% CI associated with the Wilcoxon-Mann-Whitney test to a predefined noninferiority margin (in this case 2 mg). Covariate adjusted linear models will again be applied in the event that key characteristics are significantly different between the groups.

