Sample size justification. Power for the Wilcoxon-Mann-Whitney derived noninferiority testing is based on 10,000 simulated trials. We simulated pain scores from a discrete distribution with median (interquartile range) 3 (2-5).⁶ Between the quartiles, the probability of each score was assumed constant. The distribution for each group was assumed to be the same. The sample size of n=50 per group provides 82% power to detect noninferiority in pain with a margin of 1.25. Similarly, opioid consumption was assumed to follow a truncated normal distribution with mean 2.5 mg and standard deviation 2 mg, and minimum value 0 mg. The sample size of n = 50 per group provides at least 95% power to detect noninferiority with margin 2 mg. However, to account for any unanticipated increase in variability, we will enroll 25 additional subjects in each treatment group. Therefore, we will enroll 75 subjects for each of the two treatments with primary end point values for a total enrollment of 150 subjects with a primary end point. To allow for dropouts, we request a maximum enrollment of 175 subjects. Noninferiority in pain is tested first, and if significant, noninferiority in opioid consumption is tested. Under this hierarchical testing framework, no adjustment in alpha is necessary to control Type 1 error.⁷

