10. HUMAN SUBJECTS

Inclusion criteria for the trial will be: (1) undergoing unilateral or bilateral breast surgery with at least moderate postoperative pain anticipated; (2) analgesic plan includes a single-injection peripheral nerve block(s); and (3) age 18 years or older.

Exclusion criteria for the trial will be: (1) morbid obesity as defined by a body mass index > 40 (BMI=weight in kg / [height in meters]²); (2) renal insufficiency (abnormal preoperative creatinine or eGFR); (3) chronic opioid use (daily use within the 2 weeks prior to surgery and duration of use > 4 weeks); (4) history of opioid abuse; (5) any comorbidity which results in moderate or severe functional limitation; (6) inability to communicate with the investigators or hospital staff; (7) pregnancy; (8) planned regional analgesic with perineural catheter placement; (9) incarceration; and (10) known allergy to amide local anesthetics. We will recruit a maximum of 175 subjects. Selection for inclusion will not be based on race or socioeconomic status. The study population of interest includes men and women of all races and socioeconomic status. There will be no participants from vulnerable populations, such as pregnant women, children, or prisoners.

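### Randomisation is stratified by unilateral versus bilateral surgery, but neither primary interval uses the stratum: a small loss of precision with balanced arms, and a possible opioid error if losses are uneven

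*Combined protocol and SAP*

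**What the plan says.** Section 10 admits patients "undergoing unilateral or bilateral breast surgery with at least moderate postoperative pain anticipated", and section 9 allocates them in "blocks of 4, stratified for unilateral vs. bilateral surgery". The primary aim (section 9, Statistical methods) says that a 95% interval "associated with the Wilcoxon-Mann-Whitney test will be derived for the group difference (paravertebral minus serratus) in median pain scores". The decision rule is: "If the lower limit of the 95% CI is greater than -1.25, we will conclude noninferiority". Opioid use in the "operating and recovery rooms will be tested in the same manner as pain", that is, by "comparing the limits of a 95% CI associated with the Wilcoxon-Mann-Whitney test to a predefined noninferiority margin (in this case 2 mg". I take the serratus block named there to be the Pecs-2 arm.

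Baseline characteristics are compared by Wilcoxon-Mann-Whitney and Fisher's exact tests. If a key characteristic differs at p<0.05, "these characteristics will be included as covariates in a linear model". Laterality is not named as a stratum or covariate anywhere in the analysis, and the power simulation has no laterality term. Pain is tested first, then opioid use, and both must pass.

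**The concern.** A factor is normally stratified at randomisation because it is expected to predict outcome. If it does, an interval that ignores it counts between-stratum variation that the design has already balanced. In a non-inferiority trial this costs power. The covariate rule offers no way back, since it admits only characteristics that are out of balance and blocking exists to prevent that.

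The balance is secured only at allocation. Under section 9, a subject whose misplaced block is not successfully redone leaves the study after randomisation, and the sample size section allows for dropouts. If such losses fall unevenly by laterality, the unstratified comparison has no protection.

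**Working it through.** **Inputs from section 9.** 75 per arm with a primary end point (150), maximum 175 enrolled, blocks of 4 within two strata; pain discrete with median 3 (IQR 2–5), margin 1.25; opioid normal(2.5, 2) mg truncated at 0, margin 2 mg. **Assumed, because the documents are silent:** bilateral share 10–50%; laterality effect 0–1 SD on a latent normal scale (0.5 SD is about 1.3 pain points or 0.8 mg; 1 SD about 2.4–2.6 points or 1.5–1.7 mg).

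**1. The plan's own power.** Pain was simulated with 25% of subjects spread evenly over 0–2, 25% at 3, 25% over 4–5 and 25% over 6–10. At 50 per group this gives 81.7% against the stated 82%; other readings of the quartiles give 74–89%. Opioid power is 99.95% (stated: at least 95%). At 75 per group, pain power is about 94%.

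**2. Can the covariate rule admit laterality?** Fisher's p was enumerated over every split of 150 that blocks of 4 allow. The minimum is 0.50 if a stratum has only 2 subjects, 0.68 with at least 4 per stratum, and 0.84 with at least 30 bilateral cases (14 versus 16, with 60 unilateral in each arm). Starting from 88 per arm, p<0.05 needs one-arm bilateral losses of 8 of 9, 12 of 18, 15 of 26 or 22 of 44 (10, 20, 30, 50% share), with no other losses. In practice the rule does not fire.

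**3. Intervals compared.** Unstratified: order statistics of all m·n pairwise differences, cut at mn/2 ± 1.96·√(mn(m+n+1)/12). Stratified: within-stratum differences only, weighted 1/(N_s+1), with variance Σ m_s·n_s/(12(N_s+1)).

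**4. Balanced arms, overall outcome distribution held fixed** (16,000 trials per scenario, no treatment difference):

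| Bilateral share | 10% | 20% | 30% | 50% |
|---|---|---|---|---|
| Excess opioid width, 0.5 SD | 0.9% | 1.9% | 2.6% | 3.3% |
| Excess opioid width, 1 SD | 4.0% | 7.8% | 10.7% | 13.8% |
| Pain power lost (points), 0.5 SD | 0.27 | 0.34 | 0.53 | 0.58 |
| Pain power lost (points), 1 SD | 1.06 | 1.81 | 1.98 | 1.87 |

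With r the width ratio, the opioid loss in subjects is 150·(1 − 1/r²). At 0.5 SD this runs from 150·(1 − 1/1.009²) = 2.7 to 150·(1 − 1/1.033²) = 9.4; at 1 SD from 11.3 (r = 1.040) to 34.2 (r = 1.138). Opioid power is 100% throughout. At 0.25 SD the methods do not differ materially. At a true 2 mg deficit, opioid false non-inferiority is 1.9–2.4% (0.5 SD) and 1.4–2.1% (1 SD) unstratified, against 2.2–2.8% stratified.

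**5. Balanced arms, laterality adding to the spread** (150 subjects, continuous pain scores, stratum-aligned rank interval). For a 2-point effect, pain power is 86.8% against 91.8% at 20% bilateral and 83.8% against 90.4% at 40%: losses of 5.0 and 6.6 points. For a 3-point effect at 40% it is 75.3% against 89.9%.

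**6. Uneven losses, opioid.** Assume 88 per arm with 26 bilateral, then 8 bilateral subjects lost from the Pecs-2 arm only. Bilateral shares become 26/88 = 29.5% and 18/80 = 22.5%; Fisher p = 0.38, so the covariate rule stays silent. If bilateral cases use 0.8–1.6 mg more, the comparison tilts towards Pecs-2 by about 0.07 × 0.8 = 0.06 mg to 0.07 × 1.6 = 0.11 mg. At a true 2 mg deficit, false non-inferiority is about 3–5% unstratified and 2–3% stratified (nominal 2.5%; simulation error about 0.3–0.4 points). The same losses from the paravertebral arm would push the other way.

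**7. Pain at its margin.** Differences between whole-number scores are whole numbers, so a lower limit of −1 passes the −1.25 rule and −2 fails, under either method. Assume a mean deficit of 1.25 (75% of Pecs-2 subjects worse by 1 point, 25% by 2, no cap at 10). The unstratified rule then passes roughly 8–10% of trials. Stratifying adds about 1 point at 0.5 SD and 3–4 points at 1 SD.

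**The case against.** The strongest reply is that this is too small to matter. The plan powers exactly the procedure it specifies, needs 82%, and has about 94% for pain at 75 per group. It also plans that "to account for any unanticipated increase in variability, we will enroll 25 additional subjects in each treatment group". Each treated side receives the same ropivacaine mass, so a large laterality effect on a single pain score is not evident, and section 8 reports no pilot data. Stratifying changes the estimand and, by step 7, can raise false claims on pain.

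Most of this stands and is why the point is minor. Two parts do not. Extra subjects buy precision but do nothing about uneven losses by laterality. And if laterality does matter, the plan leaves unused information that it already holds for every subject.

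A reader might infer that ignoring the stratum is always conservative and cannot produce false non-inferiority claims. The documents do not support that: they allow exclusion after randomisation, and step 6 gives an opioid counter-example. Nor can it be said of pain, where both methods exceed 2.5% in step 7; the high coverage seen with equal arms does not carry over to the margin.

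**Conclusion.** The mismatch between design and analysis is real, and the covariate rule will not repair it. With arms balanced within strata and a laterality effect of 0.5–1 SD, it costs about 1–14% of opioid interval width and roughly 0.3–2 points of pain power. The pain loss is 5–7 points if a 2-point effect adds to the spread, and more for stronger effects. With losses uneven by laterality, the opioid interval can become anti-conservative. At 0.25 SD or less with balanced arms, nothing material is lost.

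Every size rests on an assumed bilateral share and laterality effect, and the simulations assume the same treatment shift in both strata. A reader might infer that the primary analysis is invalid or the trial underpowered; neither follows. With balanced arms opioid error stays at or below nominal, and in the fixed-spread scenarios pain power stays above the planned 82%. Severity: minor.

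**What to change.** Prespecify, for both co-primaries, a laterality-stratified rank analysis (van Elteren-type test with a stratified Hodges-Lehmann 95% interval) at the stated margins of 1.25 points and 2 mg. State that it estimates a common within-stratum shift, and report the arm difference by laterality descriptively. Always include laterality in any covariate-adjusted linear model. Do not make a linear model the primary analysis: in step 5's simulations its pain power at 150 subjects was 83–86%, against 89–92% for the stratum-aligned rank interval.

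The cost is a few sentences and a short program, with no new data or patients. If laterality does not matter, stratifying costs about 0.4% of opioid width (150·(1 − 1/1.004²) ≈ 1 subject) and under 0.3 points of pain power. The change of estimand is small: with no opioid deficit in unilateral cases and 2 mg in bilateral cases, the two estimates differed by at most 0.06 mg. The plan should also disclose the step 7 cost: under the assumed shift, the narrower pain interval adds about 1 point (0.5 SD) to 3–4 points (1 SD) of false non-inferiority at a mean 1.25-point deficit.

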Single-injection blocks will be considered successful if, within 30 minutes, the subject experiences decreased sensation to cold temperature with an alcohol pad over the approximate level of the ipsilateral 4th thoracic dermatome. Misplaced blocks will be replaced successfully, or the patient excluded from further study participation. For subjects undergoing bilateral surgical procedures, a block using the same protocol will be administered on the contralateral side.

Intraoperatively, all subjects will receive a general anesthetic using inhaled and intravenous anesthetic and oxygen. Intravenous fentanyl will be administered for cardiovascular responsiveness to noxious stimuli at the discretion of the anesthesia provider.

Postop: Subjects will be discharged with a prescription for oxycodone 5 mg tablets for supplementary analgesia and instructed to record the time at which they take their first opioid tablet as well as the time at which they believe the block starts to wear off.

Outcome measurements (end points). Pain scores will be recorded using the NRS. Within the recovery room, pain scores, opioid requirements, and antiemetic administration will be recorded by nursing staff masked to treatment group. The morning following surgery, all subjects will be contacted by phone or in person [if hospitalized] to record lowest, average, highest, and current pain scores; sleep disturbances, and nausea using a 0-10 Likert scale (0 = no nausea; 10 = vomiting). For outpatients, opioid requirements will be recorded while inpatients will have opioid requirements extracted from the electronic medical record. In addition, we will extract antiemetic use from the electronic record. We will collect the times at which subjects felt their block resolve and they consumed their first opioid analgesic pills following recovery room discharge.

Hypothesis 1: Following breast surgery, **analgesia** will be non-inferior in the recovery room with a Pecs-2 block compared with a paravertebral block as measured with the Numeric Rating Scale.

Hypothesis 2: For breast surgery, **opioid** consumption will be non-inferior in the operating and recovery rooms with a Pecs-2 block compared with a paravertebral block (primary: cumulative intravenous morphine equivalents).

Primary end point: *In order to claim that Pecs-2 blocks are non-inferior to paravertebral blocks, both Hypotheses 1 and 2 must be at least non-inferior.*

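### The printed pain margin of 1.25 is applied to two different quantities, and the per-subject recovery-room score that decides what it means is not defined

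*Combined protocol and SAP*

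**What the plan says.** All of this is in section 9 of the combined protocol and SAP.

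- **Collection (Outcome measurements).** "Within the recovery room, pain scores, opioid requirements, and antiemetic administration will be recorded by nursing staff masked to treatment group". No time point is given, and no rule for reducing several readings to one. For the next-morning contact the versions are named: "to record lowest, average, highest, and current pain scores".
- **Main rule (Primary aim).** A 95% Wilcoxon-Mann-Whitney interval is formed for paravertebral minus Pecs-2 (called serratus there), described as a group difference in median recovery-room pain. Then: "If the lower limit of the 95% CI is greater than -1.25, we will conclude noninferiority".
- **Fallback (Primary aim).** "If there are significant differences between the groups in any key characteristics, these characteristics will be included as covariates in a linear model". And: "The same noninferiority margin (-1.25) will be applied to the 95% CI for the covariate adjusted group difference in mean pain".
- **Power (Sample size justification).** Pain was simulated as a discrete score with median 3 and quartiles 2 and 5, the same in both groups. "The sample size of n=50 per group provides 82% power to detect noninferiority in pain with a margin of 1.25". The plan then raises the number to 75 per group.
- **Order of testing.** "Noninferiority in pain is tested first, and if significant, noninferiority in opioid consumption is tested".

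**The concern.** A Wilcoxon-Mann-Whitney interval estimates the Hodges-Lehmann shift, which is the median of all pairwise differences between groups. The linear model estimates a difference in means. With coarse scores these can differ, and a non-integer margin such as 1.25 behaves differently on each. The plan calls it the same margin in both places.

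Pain is tested first, so this rule is the gate to the trial's claim. A baseline significance test, which can be positive by chance, decides which of the two rules applies. How far apart they are depends on whether a subject contributes one whole-number score, a median or an average, and the plan leaves that open.

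**Working it through.** **Inputs.** From the plan: quartiles 2, 3 and 5; equal probability per score between quartiles; identical groups; 95% interval; margin 1.25; n=50 (power statement) and n=75 (planned) per group. Assumed, because the plan does not give it: whole-number scores, with 25% of probability spread evenly over each of {0,1,2}, {3}, {4,5} and an upper quarter of either 6-8 (SD 2.28) or 6-10 (SD 2.70). Ranges below cover both upper quarters. The main results use 20,000 simulated trials per cell.

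**Step 1. The plan's 82%.** The lower limit is an order statistic of the n² pairwise differences, with rank n²/2 - 1.96·√(n²(2n+1)/12). For n=50 this is 1250 - 1.96×145.1 ≈ 966 of 2,500. With the 6-10 upper quarter the pass rate is 80.8-81.6%, which reproduces 82%; with 6-8 it is about 87%. Half-point, third-point, tenth-point and continuous scores gave only 70-76%.

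**Step 2. What 1.25 means there.** Differences between whole numbers are whole numbers, so the limit is a whole number. Exceeding -1.25 is therefore the same event as being at least -1, and so is exceeding -1.01, -1.5 or -1.99. Pass rates with the 6-10 upper quarter:

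| Margin | Wilcoxon n=50 | Wilcoxon n=75 | Mean difference n=50 | Mean difference n=75 |
|---|---|---|---|---|
| 1.00 | 19.5% | 26.8% | 45% | 62% |
| 1.01 | 80.8% | 93.4% | 46% | 63% |
| 1.25 | 80.8% | 93.4% | 63% | 81% |
| 1.50 | 80.8% | 93.4% | 79% | 92% |
| 1.99 | 80.8% | 93.4% | 95% | 99% |

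**Step 3. Both rules at 1.25, identical groups.** A closed-form check for the mean difference is Φ(1.25/(SD·√(2/n)) - 1.96). With SD 2.70 and n=75 the standard error is 0.441, so Φ(2.84 - 1.96) = Φ(0.88) ≈ 81%. With SD 2.28 the standard error is 0.372, so Φ(1.40) ≈ 92%. Simulation:

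| Result | n=50 | n=75 |
|---|---|---|
| Wilcoxon passes | 81-87% | 94-97% |
| Unadjusted mean difference passes | 63-78% | 80-92% |
| Wilcoxon passes, mean difference fails | 9-18% | 5-14% |
| The reverse | about 0.02% | 0 of 20,000 |

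**Step 4. A case where the two quantities separate.** Assume 75% of Pecs-2 subjects are worse by 1 and 25% by 2, with scores not capped at 10.

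- Mean difference: 0.75×1 + 0.25×2 = 1.25.
- Group medians: the paravertebral cumulative probability is 0.50 at 3. The Pecs-2 cumulative probability is 0.4375 at 4 and 0.594 at 5. The medians are 3 and 5, a difference of 2. If the exact tie at 0.50 is averaged, they are 3.5 and 5, a difference of 1.5, still beyond 1.25.
- Hodges-Lehmann shift: the probability that a pairwise difference (Pecs-2 minus paravertebral) is at most 0 is 0.41, and at most 1 is 0.53. The shift is 1.

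The Wilcoxon rule passes 10-11% at n=75 (8-9% at n=50); the mean difference passes about 2.5%. For a pure +2 shift the Wilcoxon rule passes in about 0.1% of trials.

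**Step 5. Dependence on the undefined score.** Under the same mix (n=50 and 75 together, within-subject correlation 0.5 or 0.8 assumed), the Wilcoxon rule passes 8-13% for the median of exactly three readings, 3.5-6% for medians of varying numbers of readings, and 2.3-3.5% for the median of exactly four. Per-subject averages with the mean difference pass 2.0-2.9%.

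**The case against.** **The 10-11% is not a false-positive rate of the Wilcoxon test.** A reader might infer from step 4 that the primary test has an inflated type I error. The documents do not support that. The Hodges-Lehmann shift under the mix is 1, inside 1.25, and the first whole-number shift beyond the margin is almost never passed. What stands is a mismatch of estimand: the rule is lenient on the difference in medians that the Primary aim names and on the fallback's mean, but not on the quantity its interval estimates.

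**The 5-14% is not the trial's risk.** It applies only if the fallback is triggered. Each baseline test has a nominal 5% chance of doing so. As an illustration, four independent tests (the plan's examples are age, sex, height and weight) give 1 - 0.95⁴ = 18.5%, and 0.185×5% to 0.185×14% is about 0.9-2.6% of trials at n=75. The list is open and the key characteristics are not named, so no firm total can be given. The adjusted model was not simulated; adjustment could narrow the gap. The disagreement is also nearly all in the conservative direction.

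**The mix leaves the scale.** With the 6-10 upper quarter it produces scores of 11 and 12. Capped at 10, the mean effect is 1.25 - 0.05×1.25 - 0.05×0.25 = 1.175. The 6-8 case stays on the scale and shows the same pattern.

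**The equivalence needs whole-number scores.** That is correct. The plan's plural scores, or its mention of medians, could mean a per-subject summary. Half-point scores still give one decision for margins from 1.01 to 1.49, yet the pass rate under the mix is then only 2.3-2.6%, so non-specificity alone is not the harm. This limits the size of the point, and it is also why the score must be defined.

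**Replacing ranks by means on single scores is a trade-off.** That also stands: it costs power.

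**Conclusion.** The point holds in limited form. One printed margin is attached to two quantities, and a baseline p-value chooses between them. If subjects contribute whole-number scores, the Wilcoxon rule is a lower limit of at least -1 whatever margin between 1 and 2 is printed, while the fallback is a stricter literal 1.25: 80-92% against 94-97% power at n=75 with identical groups.

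A reader might infer that the 82% is wrong or the trial underpowered. Neither follows. The 82% reproduces for the rule as written, and the Wilcoxon pain test has 94-97% power at the planned size; the 82% is simply not specific to 1.25. Nor do the pain pass rates measure a false overall claim, because opioid noninferiority is also required; they are upper limits for a false claim caused by pain.

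The figures rest on the assumed upper quarter, on single whole-number scores and on an unadjusted mean difference. The gap shrinks or disappears with summaries of several readings, which section 9 does not settle.

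**What to change.** Before outcome data are analysed:

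1. Define one recovery-room pain score per subject: which readings, how combined and to what precision. The mean of that subject's recovery-room NRS values is one example.
2. Name one estimand and apply 1.25 to it in both the main and the adjusted analysis, so that a baseline test cannot change the decision rule. The mean difference already in the plan could serve for both.
3. Re-simulate on that scale with a distribution matching 3 (2-5), and restate the power and the error rate at the margin.

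If single whole-number scores and the Wilcoxon interval are kept, say that the rule is a lower limit at or above -1 and that the 82% applies equally to any margin between 1 and 2. The adjusted analysis would still need to target the same quantity.

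Cost: a few sentences and a re-run simulation, with no additional patients. With the mean difference on single scores, power at n=75 falls from 94-97% to 80-92%. Averaging readings recovers part of this: 84-99% at n=75 (67-94% at n=50), assuming within-subject correlation of 0.5-0.8.

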9. RESEARCH DESIGN AND METHODS

This investigation will be a randomized, subject-masked, active-controlled parallel-arm, human subjects clinical trial. Of note, we will be using standard-of-care local anesthetic under an FDA-approved purpose and do not plan to research a possible change of indication or use of these medications as part of this research project. The treatments in both groups are currently used at our institution and there is true clinical equipoise at this time. The only difference in treatment between subjects who enroll versus those not enrolled in this study will be those who enroll will have the decision between which anatomic block location determined randomly, as opposed to the physician simply choosing him/herself.

Enrollment. Consenting adults undergoing breast surgery with a planned single-injection regional analgesic will be offered enrollment. Patients undergoing breast surgery with a planned perineural catheter regional analgesic will be excluded. Study inclusion will be proposed to eligible patients prior to surgery. If a patient desires study participation, written, informed consent will be obtained using a current UCSD IRB-approved ICF. Selection for inclusion will not be based on gender, race, or socioeconomic status. The study population of interest includes men and women of all races and socioeconomic status. Inclusion and exclusion criteria are listed in section #9 below.

Preoperative Procedures. Following written, informed consent, we will collect baseline anthropomorphic information (e.g., age, sex, height, and weight). All subjects will have a peripheral intravenous (IV) catheter inserted, standard noninvasive monitors applied, supplemental oxygen administered via a nasal cannula or face mask, and placed in the sitting position. Midazolam and fentanyl (IV) will be titrated for patient comfort, while ensuring that patients remain responsive to verbal cues. Both possible block locations will be viewed with ultrasound. If one or both of the locations is unacceptable for block placement in the clinician's opinion, the subject will not be

randomized and will not proceed further with the study.

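### Baseline p<0.05 tests choose the covariates and can switch the analysis of both primary end points, while the randomisation stratum is in no planned analysis

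*Combined protocol and SAP*

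**What the plan says.** All references are to Section 9 of the combined protocol and SAP.

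- **Statistical methods, opening paragraph.** "Baseline characteristics of arms will be compared using the Wilcoxon-Mann-Whitney and Fisher's Exact tests". Then: "Key characteristics that are significantly different ($p < 0.05$) will be included as covariates in the analysis models".
- **Primary aim, pain.** The deciding rule for the Wilcoxon interval has no exception attached: "If the lower limit of the 95% CI is greater than -1.25, we will conclude noninferiority". The text then continues: "If there are significant differences between the groups in any key characteristics, these characteristics will be included as covariates in a linear model". It adds: "The same noninferiority margin (-1.25) will be applied to the 95% CI for the covariate adjusted group difference in mean pain".
- **Primary aim, opioid.** The margin is 2 mg and the trigger is the same: "Covariate adjusted linear models will again be applied in the event that key characteristics are significantly different between the groups".
- **Preoperative Procedures.** The only baseline variables named are examples: "we will collect baseline anthropomorphic information (e.g., age, sex, height, and weight". Key characteristics are not listed anywhere.
- **Randomisation.** Allocation uses "blocks of 4, stratified for unilateral vs. bilateral surgery". Neither the statistical methods nor the sample size justification mentions this stratum.
- **Sample size justification.** Power is simulated for the Wilcoxon-based test only: 82% for pain and at least 95% for opioid, at 50 per group. The planned size is 75 per group.

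**The concern.** Three features combine.

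1. **The selection rule looks at the wrong thing.** Under correct randomisation every baseline difference is due to chance. A p<0.05 screen picks covariates because they happen to be imbalanced, whether or not they predict pain or opioid use. Adjustment is worth having for prognostic variables, and those can be named in advance.

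2. **The trigger changes the method and the summary measure.** The Wilcoxon interval, which the plan describes as a difference in medians, gives way to or is joined by an interval for an adjusted mean difference at the same numerical margin. The text does not say whether the second interval replaces the first, supports it, or must also pass.

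3. **The stratifier is left out.** Unilateral versus bilateral surgery is the one variable that the design treats as important enough to balance. The planned analyses ignore it, and the screen cannot realistically bring it in, because stratified blocks keep it balanced.

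At stake is whether the deciding analysis is fixed before the data are seen. Both end points must pass for the trial's claim.

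**Working it through.** **Inputs from the plan.** Pain is discrete with median 3 and IQR 2-5, the same in both arms; margin 1.25; two-sided 95% CI; 75 per arm. Opioid is truncated normal (mean 2.5 mg, SD 2 mg, minimum 0); margin 2 mg.

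**Assumptions.** Integer scores with 25% spread evenly over 0-2, 25% at 3, 25% over 4-5 and 25% over 6-10 (SD 2.70). Four baseline characteristics. Covariate correlations, stratum effect and bilateral share are also assumed; the documents give none of them.

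**1. The plan's own figure.** Simulated Wilcoxon power at 50 per arm is 80-82%, against the stated 82%. The figure is reproduced. Opioid power exceeds 99%, consistent with at least 95%.

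**2. The linear-model interval on the same scores (unadjusted).** Approximate power = Φ(1.25/SE − t), with SE = 2.70 × √(2/n).
- n = 50: SE = 0.54; 1.25/0.54 − 1.98 = 0.33; power about 63%.
- n = 75: SE = 0.44; 1.25/0.44 − 1.98 = 0.86; power about 80%.

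Simulation agrees: 63% and 80-81%. The Wilcoxon interval has 93-94% at n = 75. If both were always run at 75 per arm, they would disagree in about 13% of trials, with the Wilcoxon passing in essentially all of these. With the top quarter on 6-8 only, or with scores finer than integers, disagreement is about 5-7%.

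**3. How often the trigger fires.** With k independent tests, P = 1 − 0.95^k.
- k = 4: 1 − 0.95⁴ = 18.5%. With assumed height-weight correlation 0.4 and 2% male, about 14%.
- k = 8: 33.7%. k = 10: 40.1%.

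**4. How often the conclusion changes (replacement reading, four characteristics).** Trigger rate × disagreement:
- high end: 0.185 × 0.132 = 2.4%;
- correlated characteristics: 0.14 × 0.132 = 1.8%;
- low-disagreement scores: 0.185 × 0.05 = 0.9%.

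Simulating the whole rule gives the same order. With non-prognostic independent covariates, pain power falls from 93.2% to 90.7%; with correlated characteristics it falls from 93.5% to 91.5%. With ten characteristics the product would be 0.401 × 0.132 = 5.3%.

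**5. Error at the margin.** On continuous scores with a true shift of 1.25, false noninferiority is 2.5% for the Wilcoxon alone, 1.7-2.5% if the linear model replaces it, and 2.6-2.8% if either may pass. On integers the Wilcoxon limit is itself an integer, so exceeding -1.25 means -1 or better. A mean worsening near 1.25 then passes in about 7-10% of trials by Wilcoxon and about 2-3% by linear model. The same numerical margin is therefore not equally strict in the two branches.

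**6. The stratum.** Blocks of 4 limit imbalance to 2 per stratum. The most extreme table at 75 per arm is 2 v 0 against 73 v 75: Fisher p = 2 × (75 × 74)/(150 × 149) = 0.497. With at least 5 subjects per stratum the smallest p is 0.68. Reaching p<0.05 needs very lopsided exclusions after randomisation. Stratifying the Wilcoxon (van Elteren weights) changes pain power by −0.1 to −0.2 points with no stratum effect, +0.5 to +0.8 at an assumed 0.5 SD effect, and about +2 at 1 SD.

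**7. Opioid.** Both methods give 99.95% power at n = 50 and 100% at n = 75, with no disagreement in 2,000 trials.

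**The case against.** The best defence is that precedence is less open than it looks. The opening paragraph says that significant characteristics enter the analysis models, and a Wilcoxon interval takes no covariates. The natural reading is that the linear model takes over when triggered, with its interval and margin already written down. That largely stands. What remains is that the text never says so, and that the Wilcoxon rule is stated without exception.

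A second objection also stands: the 13% disagreement applies only if both methods are run in every trial. A reader might infer that the conclusion is in doubt in one trial in eight. It is not, because the linear model enters only when triggered.

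Third, the linear model is not simply the worse branch. Where the triggering covariate is strongly prognostic (assumed correlation 0.6 with pain), it has more power in those trials, 94% v 81%. It also protects better against a mean worsening on integer scores. Choosing the Wilcoxon as primary is a trade-off.

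A reader might also infer that the rule inflates the error rate, or that omitting the stratum invalidates the test. The documents support neither. Under the replacement reading error does not rise; even if either interval could suffice, it reaches only 2.6-2.8% against 2.5%. Ignoring a prognostic stratum widens the interval, which is conservative.

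**Conclusion.** The point holds as a defect of pre-specification with a modest numerical effect. Chance imbalance decides which covariates are used and can change the method and the summary measure for both primary end points. The covariate list is open, precedence is implied and not stated, only the Wilcoxon branch is powered, and the randomisation stratum is not analysed.

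For pain at 75 per arm with four characteristics, the rule changes the conclusion in about 1-2.5% of trials and moves power by about 2.5 points or less. Both figures grow with a longer list. Opioid conclusions do not change on the plan's assumptions. Leaving out the stratum inflates no error; including it is worth between −0.2 and +2 points of power, depending on an effect that the documents do not give. The sizes rest on the assumed number and correlation of characteristics and on one spread of integer scores that fits the plan's 82%.

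The change should be made because it is cheap and removes discretion, not because the trial's conclusion is at serious risk.

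**What to change.** 1. Delete the baseline significance tests as a rule for covariates or method. Report baseline data descriptively.
2. Keep the plan's Wilcoxon (Hodges-Lehmann) 95% CI as the single deciding analysis for pain and for opioid, stratified by unilateral/bilateral surgery, against the stated margins. Say that it decides if other analyses disagree.
3. Report beside it, as a sensitivity analysis, a linear model with treatment, stratum and a covariate list fixed in advance for prognostic value.

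**Cost.** Mainly SAP wording: the stratum is already recorded at randomisation, and the deciding analysis stays in the family used for the sample size. A sentence should note that the stated power is for the unstratified version. About 0.1-0.2 points of power are lost if the stratum is not prognostic. Adjustment for a prognostic chance imbalance becomes supportive only. On integer scores the deciding rule passes a mean worsening near 1.25 in about 7-11% of trials (11% with stratification and an assumed 1 SD stratum effect), against about 2-3% for the linear model. That is why the linear result should be shown beside it.

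**Alternative.** A pre-specified linear model as primary is legitimate if the sponsor wants protection on the mean. The pain power must then be restated: about 63% at 50 per arm and about 80% at 75 per arm, unadjusted.
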